4.3.4 Matching strategies

We will perform approximate frequency matching for recruiting control subjects using age, gender and race. The purpose of frequency matching is to ensure similar enough distributions between case and control groups to allow for appropriate statistical adjustment in the analyses. For every 30 heavy drinking controls the Data Coordinating Center (DCC) will evaluate the distribution of age (categories: 20-40, 41-60, 61-80, >80), gender, race (whites, blacks, others) overall and at each site. We will then compare that to the distributions of already recruited cases to determine if the distributions in age, gender, and race are similar. If the controls differ markedly, the DCC will instruct the coordinators to concentrate on recruiting the underrepresented groups in the control cohorts. The distribution of matching variables in the case and control groups will be re-examined periodically (approximately every 30 heavy drinking controls) and the control subjects will be recruited based on the updated distributions of demographic variables, as needed.

4.3.5 Variables and Data to be collected:

We will collect the following clinical details from subjects with AH and their controls (as appropriate). The detailed data collection and the questionnaires that we will use are outlined in the case report form (CRF).

- a) Demographics and anthropometric measures: These variables characterize the study cohort.
- b) Medical History: Detailed past medical history including prior history of AH. Specific

- attention will be paid to collecting family history of alcohol abuse and alcoholic liver disease and history of bariatric surgery.
- c) Medicinal history: A medication review of prescription and over the counter medications will be completed
- d) Detailed alcohol consumption history: We will use AUDIT, AUDIT-C and Time Line Follow-Back Questionnaires (TLFB) for quantifying alcohol consumption [11;12].
- e) Quality of life: We will use the Chronic Liver Disease Questionnaire (CLDQ) for quantifying quality of life.
- f) Signs and symptoms associated with liver disease and routine laboratories. These include the presence of ascites, jaundice, varices, and hepatic encephalopathy. Additionally, the subject's HBV, HCV and HIV status will be recorded, if available.
- g) Discriminant factor (DF), Model for End Stage Liver disease (MELD) score, and Child- Pugh score will be calculated [7].

5. STUDY PROCEDURES

The study consists of two parts, a baseline phase and a follow-up phase.

5.1Baseline Phase

All subjects:

Patients will sign the consent and data will be collected on demographics, ethnicity, clinical characteristics, alcohol history, anthropometric measures, biosamples (Plasma/serum, peripheral blood mononuclear cells [at select sites], genomic DNA, urine [when available], stool [when available], saliva and liver tissue [where available] will be collected and stored).

5.2 Follow up visits

Alcoholic hepatitis cases: will be seen at (week 4), (week 12), (week 24). During these follow-up visits, data on clinical characteristics, alcohol use, and biosamples will be obtained. If a patient misses a follow-up visit, the patient will be called and the data will be collected from their medical records (if available). Cases will then be followed until the end of study after their final visit (week 24) by checking their medical record. Vitality status will also be checked via National Death Index to ensure survival status could be collected for subjects who could not be followed through medical record review.

Heavy drinking controls without significant liver disease: The second part consists of a follow-up visit during week 24, data on clinical characteristics, alcohol use, and biosamples will be obtained.

Healthy Controls: There will be no follow-up visits

Table 2. Study procedures during the baseline and follow up visit.

Procedures	Baseline ¹	Week 4 (D15 - D56)	Week 12 (D57 - D 126)	Week 24 (D127 - D 252)	Every 24 weeks for a maximum of 5 years
Source of data	Patient visit & medical records	Patient visit, medical records ±phone call	Patient visit, medical records ±phone call	Patient visit, medical records ±phone call	Medic al Recor ds
Group	AH, Drinking Controls, and Healthy Controls	АН	АН	AH and Drinki ng Contro Is	АН
Informed Consent	X				
Demographics	X				
Anthropometric measurements	X	X	X	X	
Vital Signs	Χ	X	Χ	Χ	
Medical history	X				
Alcohol use History	X	X	Χ	X	
Questionnaires ³	Х	Χ	Χ	Χ	
Con-Med Review	Χ	X	X	X	
Events of Special Interest ⁵		Х	X	Х	
General PE	X				
PE (liver-related)		X	Χ	X	
Blood tests and other pr		1	T	Las	r
Hepatic Function	X	X	X	X	
Basic metabolic panel	X	X	X	X	
Hematology/CBC	X	X	X	X	
Coagulation/INR	X	Х	X	X	
Infection screen ²	X				
Imaging/X-ray ² Endoscopy ²	X				
Fibroscan or other ⁴	X			X	
Pregnancy Test, Urine	X	X	X	X	
Research Specimen Coll			Ι Λ	Ι Λ	
Plasma	X	Х	Х	Χ	
Serum	X	X	X	X	
Stool (when available)	X	X	X	X	
Saliva ⁶	X		X		
Urine (when available)	X	Χ	X	Χ	
Liver Biopsy (when available)	X	X	X	X	
PBMC (optional by site)	Х	Х	Х	Х	
DNA (if patient consents)	Х				
Survival, from medical records, phone call or					X
death indices					

¹For patients with AH, data obtained prior to start of treatment for AH. If patient did not receive specific treatment for AH, then data obtained as early as possible after admission to hospital. ²Data will be recorded only if it has been obtained as standard of care.

³ Questionnaires include timeline follow back (TLFB), AUDIT- C, AUDIT, and Chronic Liver Disease Questionnaire. TLFB will be the only questionnaire done at follow-up visits

⁴Assessment of liver fibrosis includes Fibroscan, ARFI, MRE and others, and will be recorded if they were performed as SOC.

 ⁵ Events of special interest include complications of liver disease, such as variceal bleeding, new/worsening hepatic encephalopathy, acute kidney injury, new/worsening ascites, and infections.
 ⁶ Saliva will only be collected until an adequate number of samples are collected from all sites.
 + Specimen collection at baseline can be collected and processed 24-48 hours after enrollment

5.2.1 Baseline Evaluations:

Prospectively enrolled patients will undergo baseline **evaluations**. The below procedures/evaluations will be performed during the baseline phase:

- Obtain Consent
- Verify Inclusion/Exclusion Criteria
- Obtain Background Information
 - Patient Profile (age, gender, race, ethnicity, etc.)
 - Complications of Liver Disease
 - Physical Examination
 - Medication Review
 - Family history of alcohol use/ complications
 - Liver Biopsy History
 - History of alcoholism counselling/treatment
- Anthropometric Measurements
- Vitals
- Timeline Follow back
- AUDIT/AUDIT-C
- Chronic Liver Disease Questionnaire
- Collect all samples below as outline in Table 2
- Collection of 60 mls of blood for research (Plasma/Serum and peripheral blood mononuclear cells [at select sites])
- Collection of 15 mls of blood for standard biochemistry tests (CBC, Platelet count, INR and CMP) if not already completed as standard of care.
- Collection of saliva
- Collection of a urine sample (when available)
- Collection of stool sample (when available)
- Collection of liver tissue (when available)
- Perform a Laboratory Examination All Subjects:

An examination of the medical record for laboratory results of the following tests will be conducted. If the laboratory tests have been completed as standard of care within the timeframe specified, those results will be used. If laboratory results are not available, these tests will be completed as part of the baseline phase.

Within 30 days of visit:

- Complete Blood Count (CBC)
- Hepatic Function
- International Normalized ratio (INR)
- Basic metabolic panel (BMP)

Optional tests: (data collected only if completed as standard of care within the timeframe specified):

- Infection screen
- Imaging/X-ray

- Endoscopy
- Fibroscan

5.2.2 Follow-up visits evaluations:

Alcoholic hepatitis subjects and heavy drinkers without clinical liver disease controls will also be seen for a follow-up visit at week 4, 12, and 24 from the date of their "baseline visit". At the follow-up visit the below procedures/evaluations will be performed.

- Physical Examination
- Medication Review
- History of alcoholism counselling/treatment
- Review of complications of liver disease
- Laboratory examination
- Anthropometric Measurements
- Vitals
- Timeline Follow back
- Collect all samples below as outlined in Table 2
- Collection of 60 mls of blood for research(Plasma/Serum and peripheral blood mononuclear cells [at select sites])
- Collection of 15 mls of blood for standard biochemistry tests (CBC, Platelet count, INR and CMP) if not already completed as standard of care.
- Collection of saliva
- Collection of a urine sample (when available)
- Collection of stool sample (when available)
- Collection of liver tissue (when available)
- Perform a Laboratory Examination All Subjects:

An examination of the medical record for laboratory results of the following tests will be conducted. If the laboratory tests have been completed as standard of care within 30 days of the visit, those results will be used. If laboratory results are not available, these tests will be completed as part of the follow up visit.

- Complete Blood Count (CBC)
- Hepatic function
- International Normalized ratio (INR)
- Basic metabolic panel (BMP)

Optional tests: (data collected only if completed as standard of care within the timeframe specified):

- Infection screen
- Imaging/X-ray
- Endoscopy
- Fibroscan

5.2.3 Exemptions to the Eligibility Criteria:

Exemptions may be allowed on a case by case basis for individuals narrowly missing the eligibility criteria. Exemptions may be sought either for cases or controls. Requests for exemptions should be initiated by the clinical center PI using an Exemptions Form which explains the rationale for seeking the exemption. Each request for the exemption will be reviewed by two investigators not associated with the site requesting the exemption. An exemption will be granted only if both reviewers agree to allow the exemption.

1. MANAGEMENT AND STORAGE OF BIOSAMPLES:

Plasma/serum, peripheral blood mononuclear cells, genomic DNA, saliva, urine (when available), stool samples (when available), and liver tissue (where available) will be collected at individual sites and shipped on a quarterly basis to be stored at the AH Tissue Bank at the University of Massachusetts until they are needed for translational studies, or the study is complete.

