4.2 Study Objectives

Primary Objectives: To collect and store clinical data to facilitate investigations of the epidemiology, diagnosis, pathophysiology, natural history, and treatment of alcoholic hepatitis.

Secondary Objectives: To develop a bio-specimen bank comprised of plasma, serum, PBMC, saliva, stool, urine, liver biopsy, DNA, and other biological specimens obtained from patients with alcoholic hepatitis, heavy drinkers without clinical liver disease, and healthy subjects to support translational research in the pathophysiology of alcoholic hepatitis.

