10. STATISTICAL ANALYSIS

Subjects' demographics, anthropometric measurements, medical history, alcohol consumption, lab test results, MELD score, quality of life, and other variables will be summarized by groups (case vs. control groups) and by visits. Mean and 95% confidence intervals will be calculated for continuous variables for each group. Proportion and frequency will be used to describe the categorical variables by groups. Two-sample t-tests will be used to compare the continuous variables and Chi-square tests will be used to compare the categorical variables by groups at each visit. Appropriate nonparametric test will be used if there is normal assumption violation. All the tests will be performed using SAS 9.3(Cary, NC).

More importantly, this aim serves as the backbone for conducting future clinical, mechanistic, biomarker discovery, therapeutic, and natural history studies. After a

structured process of requesting ancillary study proposals from consortium investigators, submitted proposals will be assessed for feasibility and scientific merit. For studies selected, a formal statistical plan will be developed that will include statistical models and methods to be used to address each specific aim of the study. Methods may be simple parametric or nonparametric methods for two-group comparisons such at t-tests or rank tests or may involve complex multivariable methods such as linear, logistic, or Poisson regression modeling. Each proposal must specify the primary and secondary outcomes. Sample size calculations associated with the primary analysis must be given, including clear specification of the outcome measure, error rates (Type I / II), minimal clinical important difference, and statistical power of at least 0.8. The expect amount and methods for dealing with missing data must be specified. Questions requiring longitudinal data analyses should apply statistical methods that account for, as applicable, time to events, repeated measurements, counts, or other discrete measurements. For time to event data, Cox proportional hazards regression model with appropriate covariates will be used. For hypotheses involving repeated measurements or discrete events, we will use either generalized linear models with generalized estimating equations or multilevel generalized linear mixed models with random coefficients.

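### Section 5.2.2's 30-day rule lets a baseline-day or other pre-window standard-of-care lab stand as an alcoholic hepatitis patient's Week 4 result, and it is not reconciled with the Table 2 visit windows

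*Combined protocol and SAP*

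**What the plan says.** Section 5.2.2 covers the CBC, hepatic function, INR and basic metabolic panel at follow-up visits. Its rule is: "If the laboratory tests have been completed as standard of care within 30 days of the visit, those results will be used". The fallback is: "If laboratory results are not available, these tests will be completed as part of the follow up visit". The procedure list in the same section makes the biochemistry draw conditional too: "Collection of 15 mls of blood for standard biochemistry tests (CBC, Platelet count, INR and CMP) if not already completed as standard of care". The research collection ("Collection of 60 mls of blood for research") carries no such condition.

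Section 5.2.1 has a parallel rule for baseline, with a timeframe of 30 days around that visit: "If the laboratory tests have been completed as standard of care within the timeframe specified, those results will be used".

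Table 2 lists the four lab groups at Baseline, Week 4 (D15–D56), Week 12 (D57–D126) and Week 24 (D127–D252), and gives both the patient visit and medical records as data sources for the follow-up columns. Footnote 1 places AH baseline data before AH treatment starts or, where no specific treatment was given, as early as possible after admission. Table 2 and the opening text of Section 5.2 give a Week 4 visit to AH cases only.

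On use of the data, the primary objective in Section 4.2 is "To collect and store clinical data to facilitate investigations of the epidemiology, diagnosis, pathophysiology, natural history, and treatment of alcoholic hepatitis". Section 10 says that "lab test results, MELD score, quality of life, and other variables will be summarized by groups (case vs. control groups) and by visits".

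**The concern.** The lab rule is measured from the visit and has no lower limit tied to baseline or to the visit window. The first follow-up visit is nominally 28 days after baseline, which is less than the 30-day allowance. Section 5.2.1 accepts a standard-of-care result for baseline on similar terms, so one result can fill both slots without any departure from the protocol. Footnote 1 makes standard-of-care labs around baseline likely in AH cases who are in hospital.

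If the same result is recorded twice, the patient shows no change from baseline to Week 4 in hepatic function, INR or metabolic panel, nor in a MELD score calculated from them. For a treated patient, a pre-treatment value then sits under a Week 4 label. The research specimen taken at the real Week 4 visit is stored beside a lab that does not belong to it. Because a qualifying result also waives the 15 mL draw, no contemporaneous study panel is taken. Natural history is part of the primary objective, and Section 10 foresees repeated-measures work, so later users of the data would inherit the error.

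**Working it through.** The plan gives no figure on this point to reproduce. The check is day arithmetic.

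**Inputs.** 30-day rule (Section 5.2.2). Windows D15–D56, D57–D126 and D127–D252 (Table 2). Nominal visits at Weeks 4, 12 and 24, which are Days 28, 84 and 168 counted from the baseline visit (Section 5.2.2).

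**Assumptions.** The documents do not say whether baseline is Day 0 or Day 1; Day 0 is used and Day 1 is also shown. They do not say whether the 30 days run backwards only or in both directions; both are shown.

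**1. Look-back at Week 4.** A lab on day L counts for a visit on day V if V − L ≤ 30.
- Nominal visit: 28 − 30 = Day −2.
- Earliest visit: 15 − 30 = Day −15, so even a pre-baseline lab qualifies.
- Latest visit: 56 − 30 = D26.

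**2. Baseline-day lab used at Week 4.** The window has 56 − 15 + 1 = 42 days.
- Baseline = Day 0: V ≤ 30, so D15–D30, which is 30 − 15 + 1 = 16 days; 16/42 = 38% of window days.
- Baseline = Day 1: V ≤ 31, so D15–D31, which is 17 days; 17/42 = 40%.

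**3. Any lab dated before the Week 4 window opens.** V − 30 < 15, so V = D15–D44, which is 44 − 15 + 1 = 30 of 42 days.

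**4. Later visits.** The earliest look-back is 57 − 30 = D27 for Week 12 and 127 − 30 = D97 for Week 24, so a baseline-day lab cannot reach either. A lab from before the window still can: for Week 12 visits on D57–D86 (30 of 70 days) and Week 24 visits on D127–D156 (30 of 126 days).

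**5. One lab serving two follow-up visits, at nominal timing.**
- Look-back only: the previous visit-day lab is reusable if the gap is at most 30 days. The gaps are 28 − 0 = 28, 84 − 28 = 56 and 168 − 84 = 84, so only baseline to Week 4 qualifies.
- Both directions: a lab serves Days 28 and 84 if L ≤ 28 + 30 = 58 and L ≥ 84 − 30 = 54, so D54–D58 serves both Week 4 and Week 12. For Days 84 and 168 it would need L ≤ 114 and L ≥ 138, which is impossible.

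**6. With the lab date held inside the Table 2 window.** Day 0 and Day 1 both precede D15, so the Week 4 visit days on which a baseline-day lab qualifies fall from 16 (or 17) of 42 to 0 of 42.

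**The case against.** The best defence is that the two sections can be read together. Table 2 puts the lab rows under a column headed D15–D56 and names medical records as a source for that column. On that reading a Week 4 lab must be both in the window and within 30 days of the visit, and a Day 0 lab is excluded. This may well be what was meant. But no section says that the windows limit lab dates. The rule written specifically for labs is in Section 5.2.2, and it counts from the visit.

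Other parts of the defence stand and limit the point:
- Reuse needs a standard-of-care lab near baseline, an early enough Week 4 visit, and a site that has, or picks, no later result.
- Section 10 compares case and control groups at each visit, but under Table 2 only AH cases have Week 4 labs. No planned between-group test is affected there. (The opening sentence of 5.2.2 also lists heavy-drinking controls at Weeks 4 and 12; that differs from Table 2, which is followed here.)
- Each ancillary study needs its own statistical plan and could set its own lab-date rule.
- The CRF and SOPs are not in the documents and may already record lab dates. That would reveal reuse but would not supply a panel that was never drawn.

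A reader might infer that the true Week 4 value is lost for good. The documents do not support that: the 60 mL research collection is unconditional, and banked plasma or serum might allow some later assays, although none is planned.

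**Conclusion.** The point holds as a gap between two rules that should be closed. Followed as written, Section 5.2.2 allows a baseline-day standard-of-care lab to be recorded as the Week 4 lab for AH visits on D15–D30 (16 of 42 window days with baseline as Day 0; 17 with Day 1). It allows some pre-window lab for visits on D15–D44. If the 30 days run both ways, a lab on D54–D58 can also serve both Week 4 and Week 12 at nominal timing.

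Two stronger readings should be resisted. The 38% is a share of window days and says nothing about the share of patients; neither the number affected nor the size of the distortion can be found from the documents. And the rule permits reuse without requiring it, since it does not say which result to take when several qualify. The harm falls on AH by-visit lab and MELD summaries and on later longitudinal or biomarker work, not on a named endpoint. It is worth correcting because the remedy is cheap and uses a draw the protocol already provides.

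**What to change.** In Section 5.2.2, keep the 30-day cap and add that:
- a standard-of-care result counts for a follow-up visit only if it is dated after baseline and inside that visit's Table 2 window (Week 4 D15–D56, Week 12 D57–D126, Week 24 D127–D252);
- a result used for one visit, including baseline, is not used for another;
- where several results qualify, the one nearest the visit and specimen date is used;
- where none qualifies, the 15 mL draw already provided for is taken;
- the lab date is recorded.

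Cross-reference Section 5.2.2 and Table 2, and state whether the 30 days run in one direction or both.

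The cost is protocol and CRF wording, a lab-date field if the CRF lacks one, and some extra 15 mL panels, mainly at Week 4. For a Day 28 visit the usable look-back falls from 30 days to 28 − 15 = 13. For a Day 84 visit it falls from 30 to 84 − 57 = 27. For a Day 168 visit it is unchanged, because 168 − 30 = D138 is already inside the window. There will be slightly more missing labs at missed visits, where data come from a phone call and the records and no fallback draw is possible. A missing value is easier to handle in analysis than a baseline value labelled as Week 4.

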2. PARTICIPANT COMPENSATION

Participant compensation is site specific.

3. PARTICIPANT RECRUITMENT

Avenues of recruitment will be site specific for example: website, flyers, social media, craigslist, studykik, newspaper, and newsletters.

4. DEVELOPMENT AND MANAGEMENT OF DATA COLLECTION

The data coordinating unit will be operated under the auspices of the Indiana CTSI [name] from the Department of Biostatistics, with an MS level biostatistician and an experienced data manager will run the data coordinating unit. The data coordinating unit will work with the steering committee and other study personnel, and will be responsible for establishing and/or conducting the following:

- Configure and set up the prospective, multicenter, observational study of patients with well characterized AH and suitable controls, within the CTMS/EDC as well as each of the smaller studies to be carried out by the consortium;
- Design specific case report forms and set up patient calendar and schedule;
- Review and test the system for the large prospective observational study and each of the smaller studies configured within the CTMS/EDC;
- Define and develop Standard Operating Procedures (SOPs) such as a process for paper- based or electronic data capture including instructions for data entry for participating sites, quality control procedures, data dictionary standards, reporting AEs/SAEs, etc.;
- Develop and implement study-specific quality assurance procedures to ensure data integrity;
- Write a data monitoring plan for the observational study and the randomized studies;

- Establish a process to facilitate/conduct audits for participating sites; audits will be done electronically and/or in person at the site, as needed;
- Provide appropriate training and/or educational material to project team members on specific aspects of each clinical study including data management and statistics;
- Prepare an implementation ("go live") plan for each study and facilitate this plan;
- In collaboration with the site study coordinators, provide assistance in the oversight of screening, enrollment, randomization, and data collection; this includes monitoring patient recruitment, compliance with visit schedules and retention.
- Coordinate periodic protocol review visits to sites on as needed basis;
- Monitor of study sites to ensure accurate execution of protocols;
- Prepare and distribute data reports to summarize performance of participating sites;
- Prepare data monitoring, performance and safety reports for interim monitoring by the steering committee, DSMB, or governmental agency;
- Submit DSMB reports of adverse events to IRBs;
- Perform final data audits and any necessary edits and prepare files for analysis;
- Coordinate data analysis with study and/or site deadlines;
- Perform appropriate statistical analyses and provide overall coordination for preparing the analysis and results needed for submitting abstracts and manuscripts
- Implement plans for final disposition of study data
- Monitor for adherence to agreed-upon patient close-out procedures

